9.3.3 Sensitivity and Supplementary Analyses of the Primary Efficacy Endpoint

Sensitivity analyses of the primary analysis of the primary efficacy endpoint is NRI-NC.

A supplementary analysis of the primary endpoint corresponded to the AO analysis specified in Section 9.2 will be performed in which all data after IE1 and IE2 will be used. CMH analysis as detailed in Section 9.1 will be repeated using AO data handling without

any imputation as an additional analysis. The analysis will be conducted on the ITT1 population who have the efficacy measurement at Week 12 visit.

9.4 Secondary Efficacy Analyses

9.4.1 Main Analyses of Ranked Secondary Efficacy Endpoints

The attributes of the estimands corresponding to the ranked secondary efficacy endpoints are summarized in [Table 2](#).

In general, secondary efficacy variables will be analyzed using the CMH test controlling for stratification factors for the corresponding period. A CMH based two-sided 95% CI for the difference between treatment groups will be constructed.

The NRI-C method will be the primary approach for missing data handling.

Table 2. Summary of the Estimand Attributes of the Key Secondary Efficacy Endpoints

Attributes of the Estimand					
	Treatment	Endpoint	Population	Handling Intercurrent Events	Statistical Summary
Secondary endpoints in the Induction Period	Each ABBV-154 group vs. placebo	Achievement of clinical remission per CDAI at Week 12 in the Induction Period, clinical remission per SF/AP at Week 12 in the Induction Period	Subjects with moderately to severely active CD who had inadequate response to or were intolerant of prior biologics	IE1: Initiation or dose escalation of CD-related confounding medications IE2: premature discontinuation of study drug All subjects will be considered as non-responders at or after IE1 All data after IE2 will be used until initiation of CD-related medications	Difference in the proportion of subjects achieving each binary secondary endpoint in the Induction Period
Secondary endpoints in the Maintenance Period	Each ABBV-154 group vs. placebo	Achievement of clinical remission per CDAI at Week 40 in the Maintenance Period, clinical remission per SF/AP at Week 40 in the Maintenance Period, endoscopic response at Week 40 in the Maintenance Period	subjects with moderately to severely active CD who had inadequate response to or were intolerant of prior biologics and achieved response after the 12-week induction treatment with ABBV-154	IE1: Initiation or dose escalation of CD-related confounding medications IE2: premature discontinuation of study drug All subjects will be considered as non-responders at or after IE1 All data after IE2 will be used until initiation of CD-related medications	Difference in the proportion of subjects achieving each binary secondary endpoint in the Maintenance Period

9.4.2 Sensitivity and Supplementary Analyses for Secondary Efficacy Endpoints

For secondary endpoints, sensitivity analysis of the of the main analysis is NRI-NC.

A supplementary analysis of secondary endpoints are AO analyses specified in Section 9.2 will be performed in which all data after IE1 and IE2 will be used. CMH analysis as detailed in Section 9.1 will be repeated using AO data handling without any imputation as an additional analysis. The analyses will be conducted on the ITT1 population (for the Induction Period)/ ITT3 population (for the Maintenance Period) who have the efficacy measurement at corresponding visit for the endpoint.

NRI-C analysis for the secondary endpoints in the Maintenance Period will also be performed the ITT3-RN population. Treatment difference between each ABBV-154 group and placebo with point estimate and 95% CI will be presented using NRI-C approach with the CMH method as detailed in Section 9.1 and Section 9.2.

9.5 Additional Efficacy Analyses

Other efficacy endpoints described in Section 3.3 will be analyzed at all visits assessed using the same methods listed in above and Section 9.2. For analyses for the Induction Period and the randomized portion of the Maintenance Period, NRI-C with CMH method will be performed for binary endpoints while MMRM/ANCOVA will be performed for continuous endpoints.

AO analyses will be performed for analyses in the Re-Induction Period.

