3.4 Additional Efficacy Endpoints

In the Induction/Re-Induction/Maintenance Periods, the additional endpoints below will be analyzed at timepoints specified in the schedule of events table of the protocol (in this section, "Baseline" refers to the Baseline [Week 0, Day 1] of the Induction Period):

- Achievement of clinical remission per CDAI.
- Achievement of clinical remission per SF/AP.
- Achievement of clinical response defined as a decrease of CDAI ≥ 100 points from Baseline (CR100).
- Achievement of clinical response per SF/AP defined as ≥ 30% decrease in average daily liquid or very soft SF and/or ≥ 30% decrease in average daily AP score and both not worse than Baseline.
- Achievement of enhanced clinical response per SF/AP defined as ≥ 60% decrease in average daily liquid or very soft SF and/or ≥ 35% decrease in average daily AP score and both not worse than Baseline, and/or clinical remission per SF/AP.

- Achievement of endoscopic remission defined as SES-CD \leq 4 and at least a 2-point reduction versus Baseline and no subscore $>$ 1 in any individual variable.
- Change from Baseline in Inflammatory Bowel Disease Questionnaire (IBDQ^{18,19}) total score.
- Change from Baseline in Functional Assessment of Chronic Illness Therapy-Fatigue (FACIT-F²⁰).
- Change from Baseline in the Bowel Incontinence Scale.
- Change from Baseline in CDAI.
- Change from Baseline in individual IBDQ domain scores (bowel, emotional, social, systemic).
- Change from Baseline in individual IBDQ items under Bowel Symptom domain (for Q1, Q5, Q9, Q13, Q17, Q20, Q22, Q24, Q26, and Q29).
- Achievement of IBDQ remission defined as IBDQ \geq 170 points.
- Achievement of IBDQ response defined as increase in IBDQ \geq 16 points from Baseline.
- Change from Baseline in 36-Item Short Form Health Survey (SF-36^{21,22}).
- Change from Baseline in fecal calprotectin (FCP).
- Change from Baseline in high-sensitivity C-Reactive Protein (hs-CRP).
- Change from Baseline in average daily AP score.
- Change from Baseline in average daily liquid or very soft SF.
- Change from Baseline in SES-CD.
- Achievement of SES-CD ulcerated surface subscore \leq 1 in each segment in subjects with a SES-CD ulcerated surface subscore \geq 2 at Baseline.
- Achievement of ulcer-free endoscopy: SES-CD ulcerated surface subscore of 0 in subjects with SES-CD ulcerated surface subscore \geq 1 at Baseline.

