7.4 Statistical Analyses for Efficacy

Efficacy analysis will be performed by the subject's randomized treatment group. All statistical tests will be performed at a 2-sided significance level of 0.1. A 95% confidence interval (CI) of the treatment difference between each ABBV-154 dose and placebo will be provided. The actual value of stratification factors will be used in the analysis.

For categorical variables, pairwise comparison will be made between each ABBV-154 dose and placebo using the Cochran-Mantel-Haenszel (CMH) test, adjusting for stratification factors (Section 5.8). Non-responder imputation incorporating multiple imputation (NRI-MI) to handle COVID-19 will be the primary approach to handle missing data for categorical endpoints.

For continuous variables, the comparison will be made between each ABBV-154 dose and placebo based on the mixed effect model repeated measures (MMRM) adjusting for visit, interaction between

treatment and visit, actual values of stratification factors as fixed factors, and baseline value (of the Induction Period) as a covariate. The MMRM will be the primary approach to handle missing values for continuous endpoints.

Summary and Analysis of the Primary Endpoint

The primary endpoint is the achievement of endoscopic response at Week 12 of the Induction Period. Comparison of the primary endpoint will be made between each ABBV-154 dose and placebo using CMH test adjusting for stratification factors. The points and CI estimate of the treatment difference for each ABBV-154 dose versus placebo will be presented.

One supplementary analysis for the primary endpoint is to test a prespecified set of dose-response models among ABBV-154 dose groups and the placebo group at Week 12 of the Induction Period using the Multiple Comparison Procedure – Modeling (MCP-Mod) method.

Summary and Analysis of Secondary Endpoints

Analysis of secondary efficacy endpoints is described above.

Summary and Analysis of Additional Efficacy Endpoints

Analysis of additional efficacy endpoints is described above.

Subgroup Analysis for Efficacy

To evaluate the consistency of efficacy across demographic and other baseline characteristics, the following subgroup analysis will be performed on the primary endpoint: Baseline glucocorticoid use (yes; no)

- Endoscopic disease severity (SES-CD < 15; SES-CD ≥ 15)
- Inadequate response to adalimumab (yes; no)
- Sex (female; male)
- Race (White; Non-white)

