9.2.3 Additional Analyses

In addition, As Observed (AO) analysis will be performed as supplementary for categorical endpoints.

- AO: The AO analysis will not impute values for missing evaluations, and thus a subject who does not have an evaluation on a scheduled visit will be excluded from the AO analysis for that visit. AO will include all values collected in the study (except data collected after initiation of ABBV-154 rescue therapy for the analyses in the Maintenance Period).

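### SAP 9.5 names only As Observed analysis for Re-Induction, although both documents make non-responder imputation the primary approach for binary endpoints

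*SAP*

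**What the plan says.** SAP 9.5 splits the methods by period. It says "For analyses for the Induction Period and the randomized portion of the Maintenance Period, NRI-C with CMH method will be performed for binary endpoints", with MMRM or ANCOVA for continuous endpoints, and then "AO analyses will be performed for analyses in the Re-Induction Period". No other method is named for Re-Induction and no reason is given.

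SAP 9.2.3 describes AO: "As Observed (AO) analysis will be performed as supplementary for categorical endpoints", and "a subject who does not have an evaluation on a scheduled visit will be excluded from the AO analysis for that visit". It also says that AO takes in every value collected, apart from data after ABBV-154 rescue in Maintenance.

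Protocol 7.4 says "Non-responder imputation incorporating multiple imputation (NRI-MI) to handle COVID-19 will be the primary approach to handle missing data for categorical endpoints". It then says "Analysis of additional efficacy endpoints is described above". Protocol 3.4 introduces that list of endpoints with "In the Induction/Re-Induction/Maintenance Periods, the additional endpoints below will be analyzed at timepoints specified in the schedule of events table of the protocol". SAP 9.2.1 likewise makes NRI-C primary for binary endpoints, without limiting it to certain periods.

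SAP 9.1 plans a comparison of Re-Induction Group 2 with Group 1. Both documents name ITT2, everyone re-randomised and dosed in that period, as the efficacy population.

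**The concern.** Re-Induction is a 1:1 randomised comparison of two active regimens in subjects who did not respond to Induction, and SAP 9.1 calls its Week 12 analysis the final efficacy analysis for the period. Under SAP 9.5 the stated population is ITT2, but the analysed set is only the part of ITT2 with an evaluation at the visit. Subjects with missing evaluations leave the denominator instead of counting as failures.

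AO also keeps responses recorded after confounding medication. Protocol 5.4 bars changes to oral glucocorticoids, aminosalicylates and immunomodulators in Re-Induction, other than mandatory tapering, and does not permit rescue there. SAP 8.1 defines confounding-medication events for Induction and Maintenance only. A response after a barred start or increase in Re-Induction would therefore count as a success. So would a response after a switch to another CD treatment following drug discontinuation, which SAP 8.2 otherwise treats as non-response.

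At stake are the reported Re-Induction response rates, the Group 2 versus Group 1 contrast, and whether those rates can be read next to the main Induction results.

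**Working it through.** **1. The plan's own figures.** The documents give no sample size, power, response rate or dropout rate for Re-Induction. The powers stated for the other periods do reproduce. For Induction (53 per group, 11% versus 37%, two-sided 0.1): (0.26 × √53 − 1.645 × √(2 × 0.24 × 0.76)) / √(0.11 × 0.89 + 0.37 × 0.63) = 1.56, which is 94.1% against a stated figure above 90%. With 40 per group in Maintenance the result is 87.1% against a stated figure above 80%. Neither bears on this point.

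**2. Which rule applies to a binary Re-Induction endpoint.**

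| Place | Rule |
|---|---|
| Protocol 7.4 with 3.4 | NRI-MI primary; additional endpoints included; Re-Induction listed |
| SAP 9.2.1 | NRI-C primary |
| SAP 9.2.3 | AO supplementary |
| SAP 9.1 | CMH in each period, with that period's stratification factors |
| SAP 9.5 | AO, with nothing else named |

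The opening sentence of SAP 9.5 refers broadly to the methods above and in 9.2. The next two sentences separate the periods, so the natural reading is AO for Re-Induction.

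**3. Relation between the two rates.** In one arm let N be the ITT2 subjects, R the observed responders, and m the fraction missing for non-COVID reasons.

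- AO = R / (N(1 − m)) and NRI = R / N, so AO = NRI / (1 − m).
- If a further fraction c is missing because of COVID-19 and is imputed at the observed rate p, then NRI-C = p(1 − m − c) + pc = p(1 − m). The relation is unchanged.
- If a fraction k of N responds only after confounding medication, and NRI-C would count these as failures, then AO = (NRI + k) / (1 − m), which is higher still.

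**4. Illustration.** All rates are assumptions. For an NRI rate of 30% with k = 0:

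| Missing (non-COVID) | AO rate | Excess over NRI |
|---|---|---|
| 5% | 0.30/0.95 = 31.6% | 1.6 points |
| 10% | 0.30/0.90 = 33.3% | 3.3 points |
| 20% | 0.30/0.80 = 37.5% | 7.5 points |
| 30% | 0.30/0.70 = 42.9% | 12.9 points |

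At 10% missing, assumed NRI rates of 11% and 37% would read 12.2% and 41.1%.

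**5. Between-group difference, with assumed missingness of 10% and 20%.**

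- NRI rates equal at 30%: AO gives 33.3% versus 37.5%, a gap of 4.2 points that comes only from unequal missingness.
- Response among evaluated subjects equal at 40%: AO gives 40% versus 40%; NRI gives 0.40 × 0.90 = 36% versus 0.40 × 0.80 = 32%.

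The two methods can disagree in either direction. Which is nearer the truth depends on why the data are missing.

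**6. Who would be missing.** Protocol 5.6 encourages subjects who stop study drug to keep attending scheduled visits, so many would stay in the denominator for symptom endpoints. The same section leaves endoscopy out of the procedures continued after stopping drug. The exposed groups are therefore study withdrawals for all endpoints and, for endoscopic endpoints, subjects who stopped drug, unless a premature-discontinuation endoscopy falls in the visit window.

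**The case against.** The strongest defence is that AO was a deliberate choice for a lower-tier analysis. Protocol 7.1 says that its methods concentrate on primary and secondary analyses and leaves full detail to the SAP. No primary or secondary endpoint lies in Re-Induction. Protocol 7.4 is worded for each dose against placebo, and Re-Induction has no placebo. ITT1 and ITT3 are called primary analysis populations, and ITT2 is not. The SAP version history records that the method in 9.5 was clarified. This softens the conflict and limits its weight, but does not remove it: Protocol 7.4 reaches the additional endpoints, Protocol 3.4 places them in Re-Induction, and the SAP's own 9.2.1 and 9.2.3 point the same way.

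A reader might also infer four stronger things that the documents do not support:

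- **That Re-Induction rates cannot be compared with Induction at all.** SAP 9.3.3 and 9.4.2 plan AO in ITT1 for the primary and secondary Week 12 endpoints, so an AO-to-AO comparison is available for those endpoints wherever they are also reported for Re-Induction. Only comparison with the main NRI-C rates is not like for like.
- **That everyone who stops drug disappears.** Protocol 5.6 keeps willing subjects in follow-up; exclusion follows a missing evaluation.
- **That AO overstates true response.** If missingness is unrelated to response, AO is unbiased and NRI is too low.
- **That AO favours the higher-dose group.** Nothing in the documents says which group would have more missing data.

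**Conclusion.** The point holds as a mismatch between SAP 9.5 and the general missing-data rule in Protocol 7.4 and SAP 9.2.1, with a predictable effect on the reported rates. AO exceeds the NRI rate by the factor 1/(1 − m) whenever an arm has at least one responder and some non-COVID missing data. On the assumed NRI rate of 30%, that is 3.3 points at 10% missing and 7.5 points at 20%. Real rates and missingness for the period are not in the documents, so these figures show scale only. Calling the excess bias against the true rate needs the further assumption that missingness is linked to non-response. The direction of any effect on the Group 2 versus Group 1 difference cannot be stated in advance.

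The change is worth making but not critical. The trial plans no overall Type I error control, and the primary and secondary results do not depend on it.

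**What to change.** - **SAP 9.5:** make NRI-C with CMH, stratified by Induction treatment group (the Re-Induction stratification factor in SAP 2.3), on ITT2 the main analysis of binary Re-Induction endpoints. Keep AO as supplementary and report missing counts by arm, with COVID-19 reasons shown separately.
- **Continuous endpoints:** state that the MMRM and ANCOVA models in SAP 9.2.2 apply to Re-Induction. That section already refers to the respective analysis period, but AO is described only for categorical endpoints, so SAP 9.5 leaves the method unclear.
- **SAP 8.1:** add an analysis definition of confounding-medication events for Re-Induction, counted from Re-Induction Baseline. Subjects who received Induction rescue enter this period by design and should not be counted as failures for that earlier use.

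The cost is SAP wording, a little extra programming of methods already specified for Induction, and one analysis definition that Protocol 7.3 does not contain for this period. Reported Re-Induction rates would be somewhat lower than under AO. No primary or secondary endpoint changes.

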9.6 Dose-Response Modeling for ABBV-154

The dose-response relationship among ABBV-154 dose groups and the placebo group will be characterized for the primary endpoint using the Multiple Comparison Procedure - Modeling (MCP-Mod) method^{5,6} among the ITT1 population for the Induction Period. The summary level response rates based on the primary analysis approach above will be used, and ADDPLAN DF software will be used to perform the MCP-Mod analyses.

A set of 6 pre-specified standardized candidate dose-response models, as described in Table 3 will be utilized to examine the dose-response relationship. A statistically significant dose-response relationship will be declared if at least one model is identified by the MCP-Mod method to be statistically significant at two-sided $\alpha = 0.1$. The fitted dose-response curves will be presented graphically for all statistically significant models along with 95% confidence bands. The minimum effective dose (MED) will be identified for each statistically significant model based on the pre-specified clinical meaningful target of 26%. The weighted MED across all significant models will be calculated, with weight being the inverse of each candidate dose-response model AIC.

Table 3. Candidate Models

Model	$f(d, \theta)$ $d = \text{dose},$ $\theta = \text{Model Parameters}$	$f^0(d, \theta)$ Standardized Model	Initial Value(s) for Parameter(s)*
Linear	$E_0 + \delta d$	D	NA
Exponential	$E_0 + E_1 \left[\exp\left(\frac{d}{\delta}\right) - 1 \right]$	$\exp\left(\frac{d}{\delta}\right) - 1$	$\delta = 1060$
Logistic	$E_0 + \frac{E_{max}}{1 + \exp\left(\frac{ED_{50} - d}{\delta}\right)}$	$\frac{1}{1 + \exp\left(\frac{ED_{50} - d}{\delta}\right)}$	$ED_{50} = 230, \delta = 101.9$
EMax	$E_0 + \frac{E_{max}d}{ED_{50} + d}$	$\frac{d}{ED_{50} + d}$	$ED_{50} = 128.9$
sigEMax	$E_0 + \frac{E_{max}d^h}{ED_{50}^h + d^h}$	$\frac{d^h}{ED_{50}^h + d^h}$	$ED_{50} = 230, h = 3.5$
Quadratic	$E_0 + \beta_1 d + \beta_2 d^2$	$d + \frac{\beta_2}{ \beta_1 } d^2$	$\delta = -0.0007$

* For Exponential model, the initial value was determined based on the assumption that ABBV-154 600 mg IV/530 mg SC EOW will achieve 95% of the maximum efficacy of ABBV-154. For Logistic, EMax, sigEMax, and Quadratic model, the initial values were determined based on the assumption that ABBV-154 600 mg IV/530 mg SC EOW and ABBV-154 300 mg IV/ 230 mg SC EOW will achieve 95% and 50% of the maximum efficacy of ABBV-154, respectively.

Steps of MCP-Mod:

1. Choose a candidate set of models as in [Table 3](#).
2. Compute the optimum contrast for each model.
3. Use contrast test to find all significant models while preserving family-wise error rate (FWER).
4. Use all significant models to make inference about the weighted target dose of interest.

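### SAP 9.6 weights the model-averaged minimum effective dose by 1/AIC, which depends on an arbitrary constant in an unnamed likelihood and not on differences in fit

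*SAP*

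**What the plan says.** Protocol 7.4 makes MCP-Mod supplementary to the primary analysis: "One supplementary analysis for the primary endpoint is to test a prespecified set of dose-response models". SAP 9.6 gives the detail.

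- **Data and software.** "The summary level response rates based on the primary analysis approach above will be used". The program named for the fits is ADDPLAN DF. No likelihood, error distribution or AIC formula is given.
- **Outputs by model.** "The minimum effective dose (MED) will be identified for each statistically significant model", for a target gain of 26 percentage points. "The fitted dose-response curves will be presented graphically for all statistically significant models".
- **Averaged output.** A weighted MED over the significant models, "with weight being the inverse of each candidate dose-response model AIC". The last step of the procedure relies on it: "Use all significant models to make inference about the weighted target dose of interest".
- **Table 3.** Six candidate shapes on the SC dose scale. The footnote says the logistic, Emax, sigEmax and quadratic starting values assume that the 530 mg and 230 mg EOW regimens "will achieve 95% and 50% of the maximum efficacy of ABBV-154, respectively".

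**The concern.** For models fitted to the same data, AIC is meaningful only up to an additive constant. Keeping or dropping terms that do not involve the model parameters shifts every AIC equally and leaves the comparison of models unchanged. A reciprocal does not respect that shift. Large positive AICs give nearly equal weights, so fit hardly counts. If all AICs are negative, the worst model gets the largest weight. If the signs are mixed, weights can be negative or above 1, and the average can fall outside the range of the individual MEDs.

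At stake is whether a prespecified dose estimate is determined by the data and the plan. As written, two analysts with the same data and the same fits can report different weighted MEDs, in a study meant to inform later dose selection.

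**Working it through.** **1. The plan's own figures.** The SAP states no figure for the weights or the weighted MED. The design inputs used below come from SAP 2.4: 53 per group, placebo 11%, a 26-point difference and two-sided alpha 0.1. They give chi-square power of 94.1%, consistent with the stated figure of more than 90%. Two Table 3 values follow from the footnote's targets: logistic δ = (530 - 230)/ln 19 = 101.9, and sigEmax h = ln 19/ln(530/230) = 3.53.

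**2. Effect of a constant shift.** The 1/AIC weight is (1/AIC_m)/Σ(1/AIC_k). The Akaike weight is exp(-Δ_m/2)/Σexp(-Δ_k/2), with Δ_m = AIC_m - AIC_min. Three models have Δ = 0, 4, 10:

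| AIC | 1/AIC weights | Akaike weights |
|---|---|---|
| 280, 284, 290 | 0.339, 0.334, 0.327 | 0.876, 0.118, 0.006 |
| 4, 8, 14 | 0.56, 0.28, 0.16 | same |
| -18, -14, -8 | 0.22, 0.28, 0.50 | same |
| -6, -2, 4 | 0.40, 1.20, -0.60 | same |

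**3. Worked example.** Assumed: rates of 11, 25, 40, 42 and 40% for placebo and Groups 1 to 4, Group 4 scored as 530, and all six models significant. The models are fitted to arm rates with a normal likelihood, v = p(1-p)/53. One AIC is misfit chi-square + 2p (p here the number of parameters). The other adds Σlog(2πv) = -18.93, the same for every model.

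| Model | MED (mg) | AIC, no constant | AIC, with constant |
|---|---|---|---|
| Linear | 502.0 | 9.15 | -9.77 |
| Exponential | 522.3 | 12.24 | -6.68 |
| Logistic | 172.8 | 8.04 | -10.88 |
| Emax | 271.6 | 6.50 | -12.43 |
| sigEmax | 157.1 | 8.04 | -10.88 |
| Quadratic | 198.6 | 6.05 | -12.88 |

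- 1/AIC without the constant: weighted MED 280.9.
- 1/AIC with it: 331.9. The worst-fitting model (exponential) gets the largest weight, 0.252, and the best (quadratic) the smallest, 0.131.
- Akaike: 238.8 both ways.

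With Group 4 scored as 265, the normal fits give 258.7, 309.8 and 225.1 respectively. Binomial fits to the same data give 286.6 (constant dropped) and 280.0 (kept) under 1/AIC, against a plain mean of 287.3 and an Akaike result of 228.1. With near-linear rates (11, 17, 25, 43, 25%) every weighting gives about 446 to 451.

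**4. Simulation.** Seven assumed curves, 2000 trials each, 53 per arm, placebo 11%, doses 0/80/230/530. Optimal contrasts for the six Table 3 shapes, with critical value 1.85. Weighted least-squares fits with assumed search ranges (ED50 0.5 to 795, h 0.5 to 10, logistic δ 5.3 to 265, exponential δ 53 to 1060). MED is the lowest dose up to 530 with a fitted gain of at least 26 points. Averages are over significant models with an MED, in trials with at least two such models (70% to 94%).

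- Generalised AIC (chi-square + 2p) and normal AIC differ by a constant within a trial. The Akaike average is identical under both; the 1/AIC average differs by a median of 4 to 147 mg.
- Under the normal form, AIC signs were mixed in 3% to 71% of trials, and the average lay outside the per-model range in 1% to 53%.
- Under binomial AIC, 1/AIC was within a median 0.1 to 2.5 mg of an equal-weight average.

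Mean weighted MED in mg, 1/AIC vs Akaike (RMSE in brackets):

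| Assumed curve (gain in points) | True MED | Binomial AIC | Generalised AIC |
|---|---|---|---|
| Emax 27.9, asymptote 30 | 181 | 227 vs 158 (101 vs 121) | 199 vs 160 (103 vs 121) |
| Emax 27.9, asymptote 32 | 121 | 208 vs 130 (120 vs 110) | 176 vs 132 (108 vs 110) |
| Emax 27.9, asymptote 34 | 91 | 198 vs 115 (130 vs 102) | 162 vs 117 (110 vs 103) |
| Emax 27.9, asymptote 38 | 60 | 183 vs 94 (137 vs 88) | 143 vs 95 (108 vs 89) |
| Emax 128.9, asymptote 40 | 239 | 278 vs 237 (95 vs 117) | 263 vs 239 (101 vs 116) |
| sigEmax, asymptote 34 | 322 | 354 vs 351 (75 vs 85) | 354 vs 352 (77 vs 84) |
| Linear, 37 at 530 | 372 | 347 vs 351 (76 vs 81) | 349 vs 352 (77 vs 80) |

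The Akaike mean is closer to the truth in 7 of 7 curves (binomial) and 6 of 7 (generalised). Its RMSE is lower in only 3 of 7 and 2 of 7.

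Five-arm runs on six of the curves, with Group 4 scored 212 (2 × 530/5, assumed), gave mixed signs in 2% to 72% of trials and averages outside the per-model range in 1% to 55%.

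**5. Two smaller points in the same section.**

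- *Emax starting value.* The 50% target at 230 needs ED50 = 230. The 95% target at 530 needs 530 × (1/0.95 - 1) = 27.9. Table 3's 128.9 is their mean. It gives 230/358.9 = 64% and 530/658.9 = 80% of maximum, so it meets neither target.
- *Group 4.* SAP 9.6 gives no analysis dose for this regimen (530 mg SC at Weeks 4 and 8 only). In five-arm data, coding it 530 instead of 212 moved the Akaike-weighted MED by a mean of 2 to 21 mg for Emax curves and 80 to 84 mg for the sigEmax and linear curves.

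**The case against.** The strongest reply is that the harm is small and the remedy not clearly more accurate. For the three simulated shapes that match Table 3 (Emax 128.9, sigEmax, linear), 1/AIC has the lower RMSE under both AIC forms. Under a binomial likelihood 1/AIC is close to equal weighting, a defensible choice and one that the fix itself adds back as a sensitivity analysis. Negative and out-of-range weights arise only under the normal form with its constant. ADDPLAN DF may fix the likelihood, and inverse AIC may be loose wording for exp(-AIC/2). The analysis is supplementary, and per-model MEDs and curves are reported anyway. For the sigEmax and linear curves, Group 4 coding matters far more than the weighting, which moves the mean by only 2 to 4 mg.

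Much of this stands. The case does not rest on uniformly better accuracy, and the low stakes limit the severity. Three parts do not answer the point.

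- The SAP does not state the software's convention, and it could not be checked from the documents.
- Fixing the likelihood would not make 1/AIC respond properly to fit. If equal weights are intended, the SAP should say so.
- If exp(-AIC/2) is intended, the text is still wrong, because read literally it gives a different number.

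The four-arm design of the main simulation is a fair criticism, but the five-arm runs show the same pattern.

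**Conclusion.** The concern holds. The weighting rule is wrong as written: it depends on an additive constant that carries no information, and depending on that constant the weights are nearly equal, reversed or invalid. The algebra is certain. The practical size is not: in the worked examples it ran from almost nil (near-linear rates) to about 51 mg (331.9 - 280.9 = 51.0; 309.8 - 258.7 = 51.1) between two AIC forms for the same fits. It depends on the likelihood and the true curve, which the documents do not give, and on the assumed rates, search ranges and Group 4 score.

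The only output affected is the supplementary weighted MED. It should be corrected, but it does not threaten the trial's main conclusions. The Emax footnote and the Group 4 coding are minor additions and do not carry the finding.

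**What to change.** In SAP 9.6:

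1. Define the weight as exp(-(AIC_m - AIC_min)/2), normalised over the significant models.
2. Name the likelihood from which AIC is computed.
3. Report an equal-weight average as a sensitivity analysis.
4. Correct the Table 3 footnote to say that the Emax ED50 of 128.9 is the average of the solutions for the two targets (230 and 27.9) and meets neither.
5. State the analysis-dose value used for Induction Group 4 on the Table 3 scale.

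This is a few sentences, to be settled before the Induction Period analysis is unblinded. It needs no new data and no change to the sample size, the MCP test or the Table 3 values. The weights are simple arithmetic on AICs already computed. The cost is a more variable weighted MED for some curves (for the Emax 128.9 curve with binomial AIC, SD 117 against 87 mg), which is why item 3 is included.
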